8.2 LISTINGS

GENERAL CHARACTERISTICS

16.2.1.1	Study and Treatment Discontinuation	RO
16.2.1.2	COVID-19-Related Comments	SAF
16.2.1.3	COVID-19-Related Remote Visits	SAF
16.2.2.1	Protocol Deviations	SAF
16.2.4.1	Demographic Data	SAF
16.2.4.2	Baseline Disease Characteristics	SAF
16.2.4.3	Concomitant Therapies	SAF
16.2.4.4	Concomitant Procedures	SAF
16.2.4.5	Rescue Therapies	SAF
16.2.4.6	Hospitalizations	SAF

Statistical Analysis Plan

ARGX-113-2002

Final Analysis

Final 5.0 of 31Jan2025

16.2.4.7 Vaccination History SAF

16.2.4.8 Procedures SAF

16.2.5.1 Administration of study drug SAF

16.2.5.2 Self-Administration of Efgartigimod PH20 SC SAF

PHARMACOKINETICS

16.2.5.3 Individual Efgartigimod Serum Concentrations and Actual Blood Sampling Times SAF

EFFICACY

16.2.6.1 MG-ADL: Total Score and Derived Variables SAF

16.2.6.2 MG-QoL15r: Total Scores SAF

16.2.6.3 EQ-5D-5L: 5 Dimensions and VAS Score SAF

16.2.6.4 [REDACTED] SAF

16.2.6.5 [REDACTED] SAF

PHARMACODYNAMICS

16.2.6.6 Total IgG SAF

16.2.6.7 Anti-AChR Antibodies SAF

SAFETY

ADVERSE EVENTS

16.2.7.1 Adverse Events SAF

16.2.7.2 Serious Adverse Events SAF

16.2.7.3 Fatal Adverse Events RO

16.2.7.4 Treatment-Emergent Adverse Events Leading to Discontinuation of Study Drug SAF

16.2.7.5 Treatment-Emergent Adverse Events Leading to Interruption of Study Drug SAF

16.2.7.6 Treatment-Emergent Adverse Events of Special Interest SAF

16.2.7.7 Injection-Related Reactions SAF

16.2.7.8 Injection Site Reactions SAF

16.2.7.9 Pneumonia-Related Adverse Events SAF

16.2.7.10 Adverse Events: Coding Information SAF

16.2.7.11 COVID-19-Related Adverse Events SAF

LABORATORY DATA

16.2.8.1 Laboratory Test Results for Subjects with Abnormal Values SAF

VITAL SIGNS

16.2.9.1 Vital Signs Results for Subjects with Abnormal Values SAF

ECG

16.2.10.1 ECG Results for Subjects with Abnormal Values SAF

SUICIDALITY ASSESSMENT

16.2.11.1 Suicidality Assessment for Subjects with Abnormal Values SAF

	Statistical Analysis Plan	
ARGX-113-2002	Final Analysis	Final 5.0 of 31Jan2025

IMMUNOGENICITY

16.2.12.1 Anti-Drug Antibodies and Neutralizing Antibodies to Efgartigimod SAF
 16.2.12.2 Antibodies and Neutralizing Antibodies to rHuPH20 SAF

PHYSICAL EXAMINATION

16.2.13.1 Physical Examination Results for Subjects with Abnormal Values SAF

9. APPENDICES

9.1 SAS CODE

9.1.1

The image consists of a series of horizontal black bars of varying lengths, set against a white background. The bars are composed of small, square pixels. They are arranged in a way that creates a stepped or ladder-like effect, with some bars extending further to the right than others. The lengths of the bars decrease as they move down the page. There are also some shorter, vertical black bars on the far left and right edges.

	Statistical Analysis Plan	
ARGX-113-2002	Final Analysis	Final 5.0 of 31Jan2025

[REDACTED]

[REDACTED]

[REDACTED]

[REDACTED]

[REDACTED]

[REDACTED]

[REDACTED]

	Statistical Analysis Plan	
ARGX-113-2002	Final Analysis	Final 5.0 of 31Jan2025

9.2 TOXICITY GRADES

Below table documents how the Common Terminology Criteria for Adverse Events CTCAE, v5.0: November 27, 2017 is implemented in the statistical analysis.

PARAMETER	Unit	GRADE 1	GRADE 2	GRADE 3	GRADE 4
Amylase (pancreatic)		>1.0-1.5 *ULN	>1.5-2.0 *ULN	>2.0-5.0 *ULN	>5.0 *ULN
Alanine amino transferase		>1-3 *ULN	>3-5 *ULN	>5-20 *ULN	>20 *ULN
Albumin	g/L	<LLN-30	<30-20	<20	-
	g/dL	<LLN-3	<3-2	<2	-
Alkaline phosphatase		>1.0-2.5 *ULN	>2.5-5.0 *ULN	>5.0-20.0 *ULN	>20.0 *ULN
Aspartate amino transferase		>1-3 *ULN	>3-5 *ULN	>5-20 *ULN	>20 *ULN
Bilirubin (total)		>1.0-1.5 *ULN	>1.5-3.0 *ULN	>3.0-10.0 *ULN	>10.0 *ULN
Calcium (ionized) low	mmol/L	<LLN-1.0	<1.0-0.9	<0.9-0.8	<0.8
	mg/dL	<LLN-4.0	<4.0-3.6	<3.6-3.2	<3.2
Calcium (ionized) high	mmol/L	>ULN-1.5	>1.5-1.6	>1.6-1.8	>1.8
	mg/dL	>ULN-6.0	>6.0-6.4	>6.4-7.2	>7.2
Calcium (corrected) low	mmol/L	<LLN-2.00	<2.00-1.75	<1.75-1.50	<1.50
	mg/dL	<LLN-8	<8-7	<7-6	<6
Calcium (corrected) high	mmol/L	>ULN-2.9	>2.9-3.1	>3.1-3.4	>3.4
	mg/dL	>ULN-11.5	>11.5-12.5	>12.5-13.5	>13.5
Cholesterol	mmol/L	>ULN-7.75	>7.75-10.34	>10.34-12.92	>12.92
	mg/dL	>ULN-300	>300-400	>400-500	>500

Statistical Analysis Plan

ARGX-113-2002

Final Analysis

Final 5.0 of 31Jan2025

Creatine kinase		>1.0-2.5 *ULN	>2.5-5.0 *ULN	>5.0-10.0 *ULN	>10.0 *ULN
Creatinine		>1.0-1.5 *ULN	>1.5-3.0 *ULN	>3.0-6.0 *ULN	>6.0 *ULN
Gamma-glutamyl transferase		>1.0-2.5 *ULN	>2.5-5.0 *ULN	>5.0-20.0 *ULN	>20.0 *ULN
Glucose (fasting) low [1]	mmol/L	<LLN-3.0	<3.0-2.2	<2.2-1.7	<1.7
	mg/dL	<LLN-55	<55-40	<40-30	<30
Lipase		>1.0-1.5 *ULN	>1.5-2.0 *ULN	>2.0-5.0 *ULN	>5.0 *ULN
Magnesium low	mmol/L	<LLN-0.5	<0.5-0.4	<0.4-0.3	<0.3
	mg/dL	<LLN-1.2	<1.2-0.9	<0.9-0.7	<0.7
Magnesium high	mmol/L	>ULN-1.23	-	>1.23-3.30	>3.30
	mg/dL	>ULN-3.0	-	>3.0-8.0	>8.0
Potassium low	mmol/L	-	<LLN-3.0	<3.0-2.5	<2.5
	mEq/L	-	<LLN-3.0	<3.0-2.5	<2.5
Potassium high	mmol/L	>ULN-5.5	>5.5-6.0	>6.0-7.0	>7.0
	mEq/L	>ULN-5.5	>5.5-6.0	>6.0-7.0	>7.0
Sodium low	mmol/L	<LLN-130	-	<130-120	<120
	mEq/L	<LLN-130	-	<130-120	<120
Sodium high	mmol/L	>ULN-150	>150-155	>155-160	>160
	mEq/L	>ULN-150	>150-155	>155-160	>160
Triglycerides	mmol/L	1.71-3.42	>3.42-5.70	>5.70-11.4	>11.4
	mg/dL	150-300	>300-500	>500-1000	>1000
Partial thromboplastin time (activated or not specified)		>1.0-1.5 *ULN	>1.5-2.5 *ULN	>2.5 *ULN	-

Statistical Analysis Plan

ARGX-113-2002

Final Analysis

Final 5.0 of 31Jan2025

CD4 count	giga/L	<LLN-0.50	<0.50-0.20	<0.20-0.05	<0.05
	counts/mm ³	<LLN-500	<500-200	<200-50	<50
Fibrinogen		<1.00-0.75 *LLN	<0.75-0.50 *LLN	<0.50-0.25 *LLN	<0.25 *LLN
International normalized ratio		>1.2-1.5 *ULN	>1.5-2.5 *ULN	>2.5 *ULN	-
Lymphocytes (absolute count) low	giga/L	<LLN-0.80	<0.80-0.50	<0.50-0.20	<0.20
	counts/mm ³	<LLN-800	<800-500	<500-200	<200
Lymphocytes (absolute count) high	giga/L	-	>4-20	>20	-
	counts/mm ³	-	>4000-20000	>20000	-
Neutrophils (absolute count)	giga/L	<LLN-1.5	<1.5-1.0	<1.0-0.5	<0.5
	counts/mm ³	<LLN-1500	<1500-1000	<1000-500	<500
Platelets	giga/L	<LLN-75	<75-50	<50-25	<25
	counts/mm ³	<LLN-75000	<75000-50000	<50000-25000	<25000
White blood cells	giga/L	<LLN-3	<3-2	<2-1	<1
	counts/mm ³	<LLN-3000	<3000-2000	<2000-1000	<1000

Note: In case ULN/LLN is higher/lower than the upper/lower limit of grade 1 (or even higher grades), ULN/LLN will be ignored and only the fixed values of CTCAE will be considered.

	Statistical Analysis Plan	
ARGX-113-2002	Final Analysis	Final 5.0 of 31Jan2025

9.3 MG THERAPIES AND PROCEDURES

Steroids	NSIDs	AChE inhibitors	Other	Procedures
PREDNISONE	CICLOSPORIN	NEOSTIGMINE	ECULIZUMAB	PLASMAPHERESIS
PREDNISOLONE	AZATHIOPRINE	NEOSTIGMINE BROMIDE	NIPOCALIMAB	THYMECTOMY
METHYL PREDNISOLONE	MYCOPHENOLATE MOFETIL	PYRIDOSTIGMINE	RITUXIMAB	ELECTRONEUROGRAPHY
HYDROCORTISONE	MYCOPHENOLATE SODIUM	PYRIDOSTIGMINE BROMIDE	IMMUNOGLOBULINS	FEEDING TUBE USER
TRIAMCINOLONE	MYCOPHENOLIC ACID	AMBENONIUM	IMMUNOGLOBULINS NOS	GASTROSTOMY ^a
DEFLAZACORT	METHOTREXATE	AMBENONIUM CHLORIDE	IMMUNOGLOBULIN THERAPY	ELECTROMYOGRAM
METHYL PREDNISOLONE SODIUM SUCCINATE	TACROLIMUS	DISTIGMINE	IMMUNOGLOBULIN HUMAN NORMAL	ENTERAL NUTRITION
PREDNISOLONE ACETATE	CYCLOPHOSPHAMIDE	DISTIGMINE BROMIDE	IMMUNOGLOBULIN G HUMAN	IMMUNOADSORPTION THERAPY
	CYTOPHOSPHANE			
	TACROLIMUS MONOHYDRATE			

^a Study physician will review case by case for this procedure to decide whether MG-related or not.

Statistical Analysis Plan

ARGX-113-2002

Final Analysis

Final 5.0 of 31Jan2025

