6.8. Concomitant Therapy

Any medication or vaccine (including over-the-counter or prescription medicines, recreational drugs, vitamins, or herbal supplements) that the participant is receiving at the time of enrollment or receives during the study must be recorded in the eCRF along with:

- Reason for use
- Dates of administration including start and end dates
- Dosage information including dose and frequency
- Brand name

The medical monitor should be contacted if there are any questions regarding concomitant or prior therapy.

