CKD-EPI	Chronic Kidney Disease Epidemiology Collaboration
CnB	cycle n baseline
CRF	case report form
CTCAE	Common Terminology Criteria for Adverse Events
DBP	diastolic blood pressure
DSMB	data safety monitoring board
ECG	Electrocardiogram
eGFR	estimated glomerular filtration rate
EoS	end of study
EQ-5D-5L	EuroQoL 5 Dimensions 5 Levels
EU	European Union
SFU	safety follow-up
gMG	generalized myasthenia gravis
HR	heart rate
ICF	informed consent form
ICH	International Council for Harmonisation
IgG	immunoglobulin G
IMP	investigational medicinal product
IP	intertreatment period
IRR	injection-related reaction

	Statistical Analysis Plan	
ARGX-113-2002	Final Analysis	Final 5.0 of 31Jan2025

ISR	injection site reaction
ITT	intent-to-treat
mITT	modified intent-to-treat
MAA	marketing authorisation application
████████	████████
MedDRA	Medical Dictionary for Regulatory Activities
MG-ADL	myasthenia gravis - activities of daily living
MG-QoL15r	15-item Quality of life scale for Myasthenia Gravis [revised version]
Nab	neutralizing antibody
NAP	not applicable
OLE	open-label extension
PK	pharmacokinetic(s)
PD	pharmacodynamic(s)
PYFU	patient years of follow-up
QTc	corrected QT interval
QTcB	Bazett's corrected QT interval
QTcF	Fridericia's corrected QT interval
RO	Rollover
SAP	statistical analysis plan
SAF	safety analysis set
SBP	systolic blood pressure
SD	standard deviation
SE	standard error
SGS CR	SGS Clinical Research
SOP	standard operating procedure
STAT	Statistics
TEAE	treatment-emergent adverse event
████████	████████
VS	vital signs
WHO	World Health Organisation
WI	work instruction

SGS	Statistical Analysis Plan	
ARGX-113-2002	Final Analysis	Final 5.0 of 31Jan2025

DEFINITION OF TERMS

AChR-Ab seronegative participants	AChR-Ab seronegative participants refers to participants in whom the anti-AChR-Ab could not be detected at screening in 1705/2001
case report form (CRF)	A printed, optical, or electronic document designed to record protocol required information to be reported to the sponsor for each trial subject.
Cohort	In the context of analysis by cohorts, cohort n is defined as all participants in at least n efgartigimod PH20 SC cycles
Display	Analysis table, figure or listing
MG therapy	Any therapy falling in one of the following categories per appendix 9.3: steroids, NSIDs or AChE inhibitors
Phase	Interval of time in the planned conduct of a study associated with a specific purpose: for example, screening, treatment, follow-up.

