3.5 PRIOR AND CONCOMITANT THERAPIES

3.5.1 *Available data*

All therapies are coded using the September 2021 version of the WHO-DRUG. ATC selection is performed. ATC coding up to level 4 is available in the clinical database. For each therapy, a start date or prior flag and stop date or ongoing flag are collected.

3.5.2 *Derivation rules*

Based on their start and stop date, therapies will be allocated to each analysis period during which they were administered. A therapy can therefore be reported in more than one analysis period.

Analysis periods are defined in section 2.2.1. Therapies with (partially) missing dates will be allocated to each period unless the available parts of the therapy start or stop date or prior and ongoing flags provide evidence the therapy was not taken during that period.

Concomitant therapies are defined as therapies taken on or after the first OLE dose date. Prior therapies are not in the scope of this interim analysis.

MG-specific therapies that were administered during the first year will be considered separately. First year is defined as the period starting from first dose in study 2002 until day 365 relative to first dose.

3.5.3 *Presentation of results*

Concomitant therapies will be tabulated, by ATC class (level 1 and level 3) and generic term. This table will be provided overall, not by cycle. The table for concomitant therapies will include MG therapies.

All concomitant therapies data will be listed with detailed information about ATC classes. Concomitant procedures will be listed separately.

For MG therapies during the first year, the number of participants per medication class (steroids, NSIDs and AChE inhibitors: appendix 9.3) and the combination of classes will be shown.

A separate listing will be created of participants receiving rescue medications. Rescue medications will be identified based on a flag on the SDTM data in the CM domain (Concomitant Medications).

Vaccination history will only be listed.

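### First-year MG therapy is identified by generic drug name alone, so a listed drug taken for another condition can be counted as gMG treatment in Tables 14.1.2.4 and 14.1.2.5

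*SAP*

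**What the plan says.** The SAP's Definition of terms describes MG therapy as "Any therapy falling in one of the following categories per appendix 9.3: steroids, NSIDs or AChE inhibitors". Section 3.5.2 adds that "MG-specific therapies that were administered during the first year will be considered separately", with the first year running from the first dose in this study to day 365. It does not say what makes a record MG-specific. Section 3.5.3 counts participants in each of the three classes and in each combination of classes, again by reference to Appendix 9.3.

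Appendix 9.3 ("9.3 MG THERAPIES AND PROCEDURES") consists of columns of generic names. The steroid column has eight entries, including hydrocortisone, triamcinolone and prednisolone acetate. The NSID (nonsteroidal immunosuppressant) column includes methotrexate, ciclosporin and tacrolimus. There is no entry for indication, route or formulation. Two further columns, for other drugs and for procedures, fall outside the MG-therapy definition. The one check of MG-relatedness is footnote a, attached to gastrostomy: "Study physician will review case by case for this procedure to decide whether MG-related or not". It governs no drug.

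On the data available, Protocol 6.8 has sites record "Reason for use" for every medication, along with "Dosage information including dose and frequency", dates and brand name. Route is not among the items named. SAP 3.5.1 states that "ATC coding up to level 4 is available in the clinical database".

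**The concern.** The label and the rule do not match. Section 3.5.2 speaks of MG-specific therapy, but a programmer following the definition would select every record of a listed drug, whatever it was given for. Several listed drugs also have uses outside gMG and exist as local products.

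Participants had to be on gMG medication at entry, so the mix of background classes is a basic description of the population. Table 14.1.2.4 (by generic term) and Table 14.1.2.5 (by class and combination) are the two final-analysis tables devoted to it. If they include use for other conditions, a reader will take the steroid and NSID classes to be larger, and treatment with an AChE inhibitor alone to be rarer, than they were.

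**Working it through.** The plan states no count or percentage for MG therapy, so there is no figure to reproduce. The check compares the texts and then bounds the effect of one misfiled participant.

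**1. What decides that a record is MG therapy**

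- Definition of terms: membership of one of three Appendix 9.3 columns. No other condition.
- Appendix 9.3: generic names only.
- Section 3.5.2: uses the term MG-specific, without a rule for it.
- Section 3.5.3: counts by the Appendix 9.3 columns.

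The operative rule is therefore a match on generic name. No minimum duration is set, so a single record in the first 365 days is enough.

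**2. Whether non-gMG use can be in the data**

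Protocol 6.8.2 allows usual treatment of other conditions unless Section 6.8.3 prohibits it. Section 6.8.3 bars starting another kind of steroid or a new NSID in year 1, but a breach does not lead to discontinuation, so the record stays in the database. Such records are possible; the documents do not say how many there are.

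**3. Direction of the error**

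Let *s* be the true share of participants using a class for gMG, and *t* the share of the remaining participants with a listed drug of that class taken for another reason. The table then shows

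*s* + (1 − *s*)*t* ≥ *s*.

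The name match can only add participants to a class. In the class table, someone already taking a steroid for gMG is not moved by a second, unrelated steroid record; only participants not otherwise in that class are. In the generic-term table, any extra listed name adds to its own row.

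**4. Size per participant**

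Input: at most 201 participants (Protocol 9.2, SAP 1.3). Under SAP 2.4.1 the denominator is the analysis set per treatment, so the total column has at most 201.

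- 1 misfiled: 1/201 = 0.4975%, about 0.5 points
- 5 misfiled: 5/201 = 2.49 points
- 10 misfiled: 10/201 = 4.98 points

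The 5 and 10 are scale markers, not estimates. A treatment column of *n* participants moves by 100/*n* points, which is more. The Japanese/non-Japanese repeats required by SAP 2.4 use the same rule with smaller denominators. Neither *s* nor *t* is in the documents, so the total overcount cannot be computed.

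**5. What else uses the rule**

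- Antibody tables by MG therapy (14.2.6.5 and 14.2.6.10): flagged in SAP 8.1 as not produced for the final analysis.
- Rescue medication: identified by a flag in the concomitant-medication data (SAP 3.5.3), not by these columns.
- IgG sensitivity analysis (SAP 4.4.3): triggered by immunoglobulin treatment or plasmapheresis, not by steroids or NSIDs.
- Hypothesis tests: none (Protocol 9.1).

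That leaves Tables 14.1.2.4 and 14.1.2.5.

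**The case against.** The strongest reply is that the plan already lets a reader see what is mixed in. Table 14.1.2.3 shows all concomitant therapy by ATC level 1, level 3 and generic term. The listing gives the ATC detail. Table 14.1.2.4 gives each generic name its own row. This has some force, but Table 14.1.2.3 covers the whole study rather than year 1 and shows no class combinations, so it cannot be used to correct Table 14.1.2.5.

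A second reply is that the design makes name matching reasonable. Participants enter on drugs from these same classes, year-1 starts of new steroids or NSIDs are barred, and deviations are tabulated. That makes a large error less likely. It does not remove the gap, because drugs for other conditions may already be in use at entry and deviations stay in the data.

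A third reply is that the term MG-specific shows a narrower intent. It does, which is a reason to write that intent into the rule.

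A reader might also infer that an adverse reaction to the study drug can alter the recorded gMG regimen, because injection reactions are treated with listed steroids. The documents do not support this. The protocol's risk table and Section 8.3.7 describe these reactions and their monitoring or reporting but mention no steroid treatment.

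**Conclusion.** The point holds as a gap in a stated rule. Followed exactly, the SAP counts any first-year record of a listed drug as gMG therapy, whatever its indication. Tables 14.1.2.4 and 14.1.2.5 can therefore overcount the steroid and NSID classes and misassign combinations, always by adding participants to a class. Each misfiled participant moves the total column by at least 1/201, about 0.5 percentage points. The total effect is unknown.

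Two stronger readings should be resisted. One is that the tables are wrong: the documents contain no count of non-gMG use, so only the possibility of an overcount is shown. The other is that study conclusions are at risk: both tables are descriptive background summaries, and no primary or secondary endpoint, rescue listing, IgG sensitivity analysis or antibody table planned for production depends on them.

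The conclusion assumes that programming follows the written definition, with no unwritten filter on indication.

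**What to change.** In the MG-therapy definition and SAP 3.5.2, state that a drug listed in Appendix 9.3 counts as MG therapy only when its recorded reason for use is gMG. Where the reason is missing or unclear, use the ATC level 4 code to exclude local products. Route should not be relied on unless it is confirmed to be collected.

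If the sponsor prefers to keep the name match, retitle Tables 14.1.2.4 and 14.1.2.5 as use of the listed drugs for any indication, with a footnote to that effect.

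Do not apply the filter to rescue therapy, which has its own flag, or to the IgG sensitivity analysis, where immunoglobulin can affect the measured IgG whatever the reason it was given.

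The cost is one or two SAP sentences, a filter on variables already collected, and probably a few records with an unclear reason to resolve before the tables are run.

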9.4 GENERAL SCHEDULE OF ASSESSMENTS

9.4.1 For Year 1

Visit Type	Treatment Period						Intertreatment Period		End of Treatment/ Safety Follow-up	End of Study	Unscheduled
	TP _n V1 ^{a,b}	PK1 ^{b,c}	TP _n V2	TP _n V3	TP _n V4	PK2 ^{b,c}	IP _n V1 ^b	IP ₀ V1 ^{a,b} / IP _n Vm ^d	ET/SFU ^{b,e}	EoS ^{b,f}	UNS ^g
Study Day (Visit Window)	A	A+2 (±1)	A+7 (±2)	A+14 (±2)	A+21 (±2)	A+23 (±1)	A+28 (±2)	Y+21 (+7)	NA	730 (±7)	NA
Informed consent	X ^h							X ^h			
Inclusion/exclusion criteria	X ^h							X ^h			
Demographic characteristics	X ^h							X ^h			
Weight	X ^h							X ^h	X	X	X
MG-ADL ⁱ	X		X ^j	X ^j	X ^j		X	X ^j	X	X	X
MG-QoL15 ^{r,k}	X		X ^j	X ^j	X ^j		X	X ^j	X	X	X
EQ-5D-5L ^k	X						X	X ^j	X	X	X
SIB risk monitoring ^o	X		X ^j	X ^j	X ^j		X	X ^j	X	X	X
Single 12-lead ECG	X						X	X	X	X	X

Statistical Analysis Plan

ARGX-113-2002

Final Analysis

Final 5.0 of 31Jan2025

Physical examination	X					X	X	X	X	X
Vital signs	X					X	X	X	X	X
Blood sampling										
Safety laboratory tests ^p	X					X	X	X	X	X
Specialty laboratory tests ^q	X					X	X			
Vaccination antibody titers and PBMCs ^r	(X)		(X)							
Immunogenicity ^s	X					X	X	X	X	X
Pharmacodynamics ^t	X					X	X	X	X	X
Pharmacokinetics ^u	X	X			X	X		X	X	X
SARS-CoV-2 test ^v										X
Urinalysis	X					X	X	X	X	X
Urine pregnancy test ^w	X					X	X	X	X	X
Efgartigimod PH20 SC administration training ^x	X		(X)	(X)	(X)	X	(X)			X

Statistical Analysis Plan

ARGX-113-2002

Final Analysis

Final 5.0 of 31Jan2025

Efgartigimod PH20 SC administration ^y	X		X ^j	X ^j	X ^j						
Administration compliance monitoring ^z	Continuous monitoring ^j										
Assessment of injection site ^{aa}	Continuous monitoring ^j										
Hospitalization monitoring ^{bb}	Continuous monitoring ^j										
Adverse events ^{bb}	Continuous monitoring ^j										
Prior/concomita nt therapy and procedures ^{bb}	Continuous monitoring ^j										

A=day 1 of a treatment period; AChR-Ab= anti-acetylcholine receptor antibody; ADA=anti-drug antibodies; AE=adverse event; eCRF=electronic case report form; EoS=end of study; EQ-5D-5L=EuroQoL 5-Dimension 5-Level; ECG=electrocardiogram; ET=end of treatment; FSH=follicle-stimulating hormone; IP_nV_m=intertreatment period (number) visit (number); MG-ADL=Myasthenia Gravis Activities of Daily Living; MG-QoL15r=Myasthenia Gravis Quality of Life 15 item scale revised; NAb=neutralizing antibody; NA=not applicable; PBMC=peripheral blood mononuclear cell; PD=pharmacodynamics; PHQ-9=9-item Patient Health Questionnaire; PH20=recombinant human hyaluronidase PH20; PK=pharmacokinetics; PKn=pharmacokinetic sample visit (number); SARS-CoV-2=severe acute respiratory syndrome coronavirus 2; SC=subcutaneous(Iv); SFU=safety follow-up; SIB=Suicide Ideation and Behavior; SoA=schedule of assessments; TP_nV_n=treatment period (number) visit (number); UNS=unscheduled; (X)=optional activity, only done under specified conditions; Y=previous intertreatment period visit

Note: All activities will be performed predose on dosing days, unless otherwise indicated.

^a The transition from the antecedent studies ARGX-113-1705 or ARGX-113 2001-to study ARGX-113-2002 can either be IP0V1 or TP1V1, depending on the need for retreatment. The first visit of study ARGX 113 2002 will always coincide with the last visit from studies ARGX 113 2001 or ARGX 113 1705.

Overlapping activities performed for the last visit of these antecedent studies will not be repeated for the first visit of ARGX 113 2002.

^b This visit must always be performed at the site. All other visits can be performed by phone if IMP administration occurs at home.

^c These are optional visits to collect additional PK samples from consenting participants. These additional visits can only be performed when all of the injections of that treatment cycle are given at the site. Sampling will only be performed during a participant's first and/or second treatment cycles.

^d These IP visits will occur every 21 days. The visit denominator ("m") will start at 2 for each IP after a TP. At each of these IP visits performed on-site, an evaluation of the need for retreatment will be done prior to performing any activities so that only activities listed for IPnVm or TPnV1 are performed. The first of these IP visits will occur on-site and the next IP visit may be done by phone. All subsequent IP visits may alternate between on-site visits and phone visits. If activities at an IP visit performed by phone indicate a need for retreatment, then a TPnV1 visit will be scheduled.

ARGX-113-2002

Statistical Analysis Plan

Final Analysis

Final 5.0 of 31Jan2025

^a For participants who discontinue early from the study, the activities will depend on the visit at which the participant had to discontinue. Participants who discontinue early from the study at either a TP visit or an IP visit should perform planned activities for the ET visit if 49 (± 2 days) days has not elapsed since the last dose of efgartigimod. These participants will not receive any further administration of efgartigimod PH20 SC during the study and will return for the SFU visit 49 ± 2 days after the last dose administration. If 49 ± 2 days has already elapsed since the last administration of efgartigimod PH20 SC, then this visit becomes the SFU visit and the SFU visit activities must be performed. Participants who discontinue early from the study between visits should perform the SFU visit at least 49 ± 2 days after the last dose administration. If 49 ± 2 days has already elapsed since the last administration of efgartigimod, then the SFU visit will be planned as soon as possible.

^f The study will last for 2 years from the participant's first visit in this study. If efgartigimod becomes commercially available for patients with gMG or available through another patient program for gMG, participants will have the choice to switch to 1 of these options after 1 year of participation in this long-term safety study. No treatment-free follow-up will be performed in this study, except for participants who do not want to continue receiving efgartigimod.

^g A UNS visit can occur at the request of the participant or the investigator. During the UNS visit, activities indicated in the SoA can be performed at the discretion of the investigator, depending on the reason for the UNS visit.

^h These activities are only performed at study entry.

ⁱ It is recommended to perform the MG-ADL scale prior to all other activities.

^j When a visit is performed by phone, only these activities must be performed.

^k These activities will only be performed in the first year of the study for each participant.

^l [REDACTED]

^m [REDACTED]

ⁿ [REDACTED]

^o The SIB Risk Monitoring assessment is based on question 9 of the PHQ-9.

^p Blood samples for clinical laboratory (hematology/clinical chemistry and FSH, if applicable) safety assessments will be collected. See Section 10.2. On dosing days, the samples will be taken predose. Participants will need to be fasted for each on-site visit at which safety laboratory assessments are collected. Fasted is defined as no food or drink at least 8 hours prior to each sampling. Permitted medications that the participant normally takes can be taken as usual before a visit.

^q Samples for specialty laboratory tests will be taken at the baseline, the IP₁V1 visit, and the next on-site visit that is at least 4 weeks after the participant's fourth dose (TP₁V4). See Section 10.2.1.

^r Additional blood samples (serum/PBMC) may need to be taken for additional/optional/future/vaccination research if the participant consents. If a participant that consents to this additional sampling receives a vaccination during the study, a baseline serum sample prior to the vaccination will be taken and a serum sample will be taken at least 4 weeks after the vaccine was administered. The closest visit that is at least 4 weeks after the vaccine was administered may be used. If this visit does not coincide with IP₁V1, then another sample will also be taken at this visit. Serum samples only need to be taken when a vaccination is planned or after a vaccination has occurred. In addition, a whole-blood sample to isolate PBMCs will be collected at study entry and then approximately every 3 months throughout the study during a scheduled on-site visit, regardless of the vaccines a participant has received.

^s Titers of ADA and the presence of NAbs against efgartigimod will be measured in serum. Blood samples for plasma titer levels of ADA and NAbs against rHuPH20 will also be taken. A titer for ADA and the presence of NAbs against PH20 must be measured at study entry for participants coming from ARGX-113-1705. If no sample is taken, the reason will be recorded.

^t The PD assessments comprises levels of total IgG, and autoantibody levels (AChR-Ab levels for AChR-Ab positive participants).

^u The PK assessments will only be taken at TP1V1. The assessment should be performed predose.

Statistical Analysis Plan

ARGX-113-2002

Final Analysis

Final 5.0 of 31Jan2025

